10.2. Management of Liver Enzyme Elevations

The FDA Guidance for Industry for Drug Induced Liver Injury (*FDA*, 2009) will provide guidance for the management of changes in liver transaminases (ALT/AST) and total bilirubin.

The following close observation guidelines will apply to subjects for whom the repeat assessment shows persistent elevations of transaminases, but who do not meet drug discontinuation criteria, and for subjects who discontinue study drug due to ALT/AST elevations.

The protocol also includes an algorithm to respond to changes in liver enzymes and functions as follow:

- To establish a baseline utilizing at least 2 lab values at least several weeks apart
- For subjects with elevated baseline liver chemistry that develop AST or ALT elevations $2 \times$ baseline, subjects will be reassessed promptly (eg, 48–72 hours) with full liver biochemistry and physical exam and if the repeat assessment shows persistent elevations in transaminases, subjects should be followed according to the “close observation” guidelines:
 - Repeat liver enzyme and serum bilirubin tests two or three times weekly. Frequency of repeat testing can decrease to once a week or less if

- abnormalities stabilize or the trial drug has been discontinued and the subject is asymptomatic.
- Collect additional PK samples at the same visits as safety labs
 - Obtain a more detailed history of symptoms and prior or concurrent diseases.
 - Obtain a history of concomitant drug use (including nonprescription medications and herbal and dietary supplement preparations), alcohol use, recreational drug use, and special diets.
 - Rule out acute viral hepatitis types A, B, C, D, and E; autoimmune or alcoholic hepatitis; NASH; hypoxic/ischemic hepatopathy; and biliary tract disease.
 - Obtain a history of exposure to environmental chemical agents.
 - Obtain additional tests to evaluate liver function, as appropriate (eg, INR, direct bilirubin).
 - Consider gastroenterology or hepatology consultations.
 - Consider liver biopsy for any patient with persistent evidence of liver injury.
- For subjects with alkaline phosphatase (ALP) elevations of $2 \times$ ULN, subjects will be reassessed promptly (eg, 48–72 hours) with full liver biochemistry and physical exam. Labs should be repeated until resolution. Above guidelines for close monitoring should also apply.
 - If a subject lives in a remote area, they can be tested locally with the results promptly communicated to the Investigator site

11. STATISTICAL CONSIDERATIONS

11.1. General Considerations

All data will be mapped into the appropriate Study Data Tabulation Model (SDTM) domains per version 3.2. All analysis datasets will be in the appropriate Analysis Data Model (ADaM) data structure. Pinnacle21 will be used to ensure compliance of the SDTM domains and ADaM datasets to Clinical Data Interchange Standards Consortium (CDISC) standards.

All quantitative endpoints will be summarized using an 8-number summary (n, mean, standard deviation, median, 25th quartile, 75th quartile, minimum and maximum values). All qualitative endpoints will be summarized by the number of subjects meeting the endpoint and the percentage of subjects out of the appropriate population. The denominator will be displayed when needed.

Statistical inference will be performed as appropriate. Only two-sided test with an $\alpha = 0.05$ will be used.

11.2. Sample Size Considerations

Group sample sizes of 44 (in each dose group) and 22 placebo subjects achieves 80.438% power to reject the null hypothesis of equal means when the population mean difference in ALT is $(-40.0) - (-10.0) = -30.0$ with a standard deviation for both groups of 40.0 and with a significance level (alpha) of 0.050 using a two-sided two-sample equal-variance t-test. To account for a 20% discontinuation rate, 15 additional subjects will be enrolled to attempt to have at least 110 subjects who complete treatment bringing the total number of subjects enrolled to 125.

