Pharmacokinetic Analyses: Plasma PK parameters for each dose level will be calculated from the concentrations of EDP-305 and its major metabolites measured in predose and postdose plasma samples. For each EDP-305 dose level, descriptive statistics (sample size, arithmetic means, geometric means, standard deviation (SD), % coefficient of variation, minimum, median, and maximum) will be presented. Figures will be created to display mean and individual subject EDP-305 concentration time curves in plasma on both a linear and logarithmic scale. The PK

parameters AUC_{0-t} , C_{max} , and T_{max} will be calculated as indicated for plasma EDP-305 and its major metabolites.

Sample Size Consideration: Group sample sizes of 44 (in each dose group) and 22 placebo subjects achieves 80.438% power to reject the null hypothesis of equal means when the population mean difference in ALT is $(-40.0) - (-10.0) = -30.0$ with a standard deviation for both groups of 40.0 and with a significance level (alpha) of 0.050 using a two-sided two-sample equal-variance t-test. To account for a 20% discontinuation rate, 15 additional subjects will be enrolled to attempt to have at least 110 subjects who complete treatment bringing the total number of subjects enrolled to 125.

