5.6. Treatment Assignment/ Randomization

Subjects will be randomized to study treatment using an Interactive Web Response System (IWRS). [REDACTED]

[REDACTED] Subjects will be randomized to the treatment groups shown below:

- Treatment Group 1 (N=50); EDP-305 1 mg orally for 12 weeks
- Treatment Group 2 (N=50); EDP-305 2.5 mg orally for 12 weeks
- Treatment Group 3 (N=25); Placebo (PBO) orally for 12 weeks

[REDACTED] The randomization code will be produced by Enanta (or designee). The Enanta unblinded biostatistician or designee will review and approve the final randomization list.

During the Screening period, subjects will be identified by a unique screening number assigned by the clinical site. Subjects who have completed screening assessments and are eligible for participation in the study will be randomized before the first dose of study drug (Day -1 or Day 1) and assigned a unique subject number which will be used to identify the subject throughout the study.

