7.1.4. Treatment Period Visits (Day 3, Weeks 2, 4, 8, and 12/EOT)

All subjects will be requested to return to the clinic on Days 3, and Weeks 2, 4, and 8 for on-treatment study visits. Subjects will be instructed to fast overnight for a minimum of 8 hours prior to each visit. Except for days when there is a clinic visit, subjects will take their daily dose of study drug at home. Treatment period assessments are listed in Table 19.

At the end of the treatment period, subjects will complete the EOT visit. Subjects who complete 12 weeks of treatment will complete the EOT assessments at the Day 84 (Week 12) visit. Subjects who discontinue treatment early should complete EOT assessments at the time of discontinuation (if in the clinic) or as soon thereafter as possible if the subject discontinues treatment while not in the clinic. Procedures performed are specified in the SoA (Table 19).

Subjects should discontinue drug on Day 84. Subjects, who return for their EOT Visit after Day 84, should stop dosing on Day 84 (Week 12 Visit).

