7.2.1. Withdrawal Criteria

Subjects may be discontinued from the study at any time if the subject, Investigator or Sponsor determines that it is not in the best interest of the subject to continue participation. Reasons for discontinuation include:

- Adverse Event
- Noncompliance with study drug dosing or study procedures
- Lack of efficacy
- Lost to follow-up
- Withdrawal by subject
- Protocol deviation
- Pregnancy
- Sponsor's decision to terminate the study
- Other

Subject-specific stopping rules due to AEs and/or laboratory abnormalities are outlined in Section 10.1.

Subjects who prematurely withdraw from the study for any reason after having been randomized will not be replaced.

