11.5. Efficacy Endpoints

11.6. Primary Efficacy Endpoints

The primary efficacy endpoint of the study is the change from baseline in ALT at Week 12. All subjects in the efficacy population will be included. Comparisons of treatment arms will be performed using an analysis of covariance (ANCOVA) model with treatment and baseline values included in the model where appropriate. Multiple Imputation (MI) will be used to impute missing data. Details will be provided in the SAP.

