5 SAMPLE SIZE AND POWER

Group sample sizes of 44 (in each dose group) and 22 placebo subjects achieves 80.438% power to reject the null hypothesis of equal means when the population mean difference in ALT is $(-40.0) - (-10.0) = -30.0$ with a standard deviation for both groups of 40.0 and with a significance level (alpha) of 0.050 using a two-sided two-sample equal-variance t-test. To account for a 10% discontinuation rate, 15 additional subjects will be enrolled to attempt to have at least 110 subjects who complete treatment bringing the total number of subjects enrolled to 125.

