7.3 Handling of missing data and outliers

7.3.1 Missing data analysis methods

In general, missing data for the primary endpoint and secondary endpoint are not imputed, with the exception being a secondary analysis on the primary endpoint. The extent and pattern of missing data for primary endpoints will be summarized by treatment group. All missing Week 12 values for the primary efficacy endpoint will be estimated by multiple imputation (MI). The Markov Chain Monte Carlo (MCMC) method (*Dong et al, 2013*) will be used to impute the missing Week 12 values. The least squares mean and standard error for the change from Baseline in Week 12 analysis values will also be derived from an analysis using the MCMC method of MI.

Multiple Imputation Method

MI handles missing data in three steps:

Step 1: Imputation using MCMC Method

For MI analysis first uses MCMC method to impute the missing data through SAS Proc MI. The goal of the imputation step is to draw random samples of missing data based on information contained in the observed data. Since the parameter (θ) of the data is also unknown, the imputation step actually draws random samples of both missing data and θ based on the observed data.

The MCMC method draws samples in two steps. At step one (I-Step), given the current estimate of $\theta(t)$ at the t^{th} iteration, a random sample Y_{miss}^{t+1} is drawn from the conditional predictive distribution of $P(Y_{mis}|Y_{obs}, \theta^t)$. At step two (P-step), given Y_{miss}^{t+1} , a random sample of $\theta^{(t+1)}$ is drawn from the distribution of $P(\theta|Y_{obs}, Y_{mis}^{t+1})$. Starting with an initial value $\theta^{(0)}$ (usually an arbitrary guess), MCMC iterates between the I-step and the P-step, leading to a Markov Chain:

It can be shown that this Markov Chain converges in distribution to $P(\theta, Y_{mis}|Y_{obs})$. It follows that the sequence $\theta(1), \theta(2), \dots, \theta(t), \dots$ converges to $P(\theta|Y_{obs})$ and the sequence $Y_{mis}^1, Y_{mis}^2, \dots, Y_{mis}^t, \dots$ converges to $P(Y_{mis}|Y_{obs})$. Thus, after the Markov Chain converges,

m draws of Y_{mis} can form m imputations for the missing data. At the end of the first step in MI, missing data will be imputed m times to produce m sets of complete data.

Step 2: Statistical Analysis

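### At the protocol's 20% discontinuation rate, 125 enrolled leaves about 100 completers, not 110; the SAP gives 10% with the same totals

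*Protocol*

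**What the plan says.** Protocol 11.2 powers each dose-versus-placebo comparison of ALT change on 44 versus 22 subjects: difference 30, SD 40, two-sided alpha 0.05, equal-variance t-test, stated power 80.438%. It then moves from 110 to 125 subjects: "To account for a 20% discontinuation rate, 15 additional subjects will be enrolled to attempt to have at least 110 subjects who complete treatment". The synopsis has the same step at the same rate: "To account for a 20% discontinuation rate, 15 additional subjects will be enrolled". SAP 5 prints it with another rate and otherwise the same figures: "To account for a 10% discontinuation rate, 15 additional subjects will be enrolled".

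Protocol 5.6 sets the arms at 50, 50 and 25; the smallest is "Treatment Group 3 (N=25); Placebo (PBO) orally for 12 weeks". Protocol 7.2.1 rules out making up losses: "Subjects who prematurely withdraw from the study for any reason after having been randomized will not be replaced".

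How a loss affects the analysis depends on the missing-data rule, and here too the documents differ. Protocol 11.6 says "Multiple Imputation (MI) will be used to impute missing data". SAP 7.3.1 says "In general, missing data for the primary endpoint and secondary endpoint are not imputed", apart from a secondary analysis of the primary endpoint. SAP 8.6.2 accordingly lists multiple imputation as an additional analysis of ALT.

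**The concern.** This sentence is the only stated reason for enrolling 125 rather than 110. Under the protocol's own rate it does not deliver the completers it names. The SAP changes the rate without changing any figure that depends on it, and SAP 9, which records changes from the protocol, does not list the change. All three places agree on the target (110) and the enrolment (125). What cannot be read from them is the loss the trial was planned to absorb, and so whether about 100 or about 112 completers should be expected.

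At stake is whether the trial keeps the 80% power it claims for its primary efficacy endpoint. If 20% is the real planning assumption and discontinuers have no Week 12 ALT, it falls below that figure on the stated test.

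**Working it through.** **Inputs.** Difference 30, SD 40, alpha 0.05 two-sided, 44 versus 22, stated power 80.438%, 15 added, 110 completers, 125 enrolled (Protocol 11.2, SAP 5). Discontinuation 20% (Protocol synopsis and 11.2) or 10% (SAP 5). Arms 50/50/25 (Protocol 5.6). No replacement (Protocol 7.2.1).

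**1. The plan's power figure.** The noncentrality is 30 / (40 × √(1/n₁ + 1/n₂)), on n₁ + n₂ − 2 degrees of freedom.
- 44 versus 22: 30 / (40 × √(1/44 + 1/22)) = 2.872 on 64 df, power 80.76%.
- 43 versus 22: power 80.438%, the printed value.

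The printed power is therefore essentially right for 44 versus 22. The fault is confined to the inflation step.

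**2. Completers from 125.**
- At 20%: 50/50/25 × 0.8 = 40/40/20 = 100.
- At 10%: 125 × 0.9 = 112.5.
- Largest rate that still leaves 110: 15/125 = 12%.

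**3. Enrolment needed for 110 completers.**
- At 20%: 110/0.8 = 137.5, so 138. Even the cruder 110 × 1.2 gives 132. Neither is 125.
- At 10%: 110/0.9 = 122.2, so 123. Here 125 is enough.

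**4. Power on the same t-test if discontinuers give no Week 12 ALT and loss is proportional across arms.**

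| Discontinuation | Evaluable, dose vs placebo | Power |
|---|---|---|
| 10% | 45 vs 22.5 | 81.6% |
| 12% | 44 vs 22 | 80.8% |
| 20% | 40 vs 20 | 76.8% |

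**5. Chance of at least 110 completers from 125** (binomial, independent discontinuation assumed): 1.3% at 20%, 57% at 12%, 82% at 10%.

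**6. How far the 76.8% depends on its assumptions.** Neither input below is given in the documents, so ranges are shown.
- *Share of the 25 expected discontinuers who still give a Week 12 ALT.* At 0%, 100 are evaluable and power is 76.8%. At 25%, 106.25 and 79.4%. At 40%, 100 + 10 = 110 and 80.8%.
- *Baseline adjustment at 40 versus 20.* The residual SD is 40 × √(1 − r²), with r the baseline-change correlation. For r = 0, 0.2, 0.28 and 0.4, power is 76.8%, 78.5%, 80.1% and 83.6%.

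**The case against.** The strongest reply is about consequence. The protocol only attempts 110 completers. The printed power is conditional on 44 versus 22 and is sound. The worst case is about 4 points per comparison in a Phase 2 dose-ranging study, with no bias and no effect on type I error. ANCOVA or late discontinuers could win those points back. All of that stands as a limit on size. It does not make the target attainable at 20%, and the trial was sized on an unadjusted t-test with no credit claimed for baseline adjustment.

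The late-discontinuer argument is also weaker than it looks. Protocol 7.1.4 says "Subjects who discontinue treatment early should complete EOT assessments at the time of discontinuation", or as soon afterwards as possible. The SAP 7.2 window for Week 12 runs from Day 71 to 7 days after end of treatment, so in general only subjects stopping at about Day 64 (71 − 7) or later would contribute a value.

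Two further points stand as caveats. First, SAP 1 was written against protocol version 3.0 (Amendment 2.0), and the version page of the protocol at hand was removed. A version difference might explain 20% against 10%. It would not repair the protocol's sentence, which fails without reference to the SAP. Second, much of the Phase 1 section and parts of the design and dose rationale are redacted, so one can say only that no basis for either rate is visible.

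**Conclusion.** The concern holds. At the protocol's 20%, 125 enrolled gives about 100 completers, 10 short of the stated target, and no usual inflation rule turns 110 into 125 at that rate. The SAP's 10% is consistent with 125 and 110, so the documents contradict each other on the rate. They do not say which was intended.

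The shortfall in completers is plain arithmetic and needs only the stated rate and the no-replacement rule. The power loss, from 80.8% to 76.8%, is moderate and is not a forecast. It rests on equal proportional loss across arms, no Week 12 ALT from discontinuers, and no gain from baseline adjustment. It matters more under the SAP, whose main ALT analysis uses observed values, than a reader of the protocol's imputation sentence would expect.

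**What to change.** Use one discontinuation rate, with its basis, in the Protocol synopsis, Protocol 11.2 and SAP 5, and restate the figures that depend on it.

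- **Option A, keep 20%.** Suggested text: *With 20% discontinuation, 125 enrolled gives about 100 completers (40/40/20); the same t-test then has about 77% power if discontinuers provide no Week 12 ALT.* The claim of at least 110 completers is removed.
- **Option B, state 10% (at most 12%).** Give the reason for the rate in all three places. The 15, 110 and 125 stay, as does power of about 80%.

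Keeping both 20% and 110 completers would take about 138 enrolled. The sponsor may choose that, but correcting the text does not require it.

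Either option costs wording in three places, with no change to enrolment, test, alpha, population or endpoint. Under Option A the stated power drops by 3 to 4 points. If the rate was changed on purpose between the documents, record that in SAP 9.

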11.3. Analysis Populations

The following analysis populations are planned:

- **Safety Population:** All subjects who receive at least one dose of study medication. Subjects will be included in the treatment group that corresponds to the study medication received during the study.
- **Efficacy Population:** All subjects who receive at least one dose of study medication. Subjects will be included in the randomized treatment group.
- **Pharmacokinetic Population:** All subjects receiving active study medication and having any measurable plasma concentration of study medication at any timepoint.

11.4. Subject Disposition and Demographic Data

The number of subjects screened, randomized, randomized and treated, randomized and not treated, in the safety population, in the efficacy population, and in the PK population will be summarized. The denominator for the calculation of percentages will be from the number of subjects randomized.

The following categories will also be summarized for subject disposition:

- Completed study drug per protocol

- Discontinued study drug early and the reason for discontinuation
- Completed the study
- Discontinued from the study early and the reason for discontinuation

Subject demographics will be summarized by randomized treatment group for all subjects in the safety population. Appropriate baseline characteristics will be included in addition to demographic characteristics. No statistical testing will be performed. Additional details will be provided in the Statistical Analysis Plan (SAP).

11.5. Efficacy Endpoints

11.6. Primary Efficacy Endpoints

The primary efficacy endpoint of the study is the change from baseline in ALT at Week 12. All subjects in the efficacy population will be included. Comparisons of treatment arms will be performed using an analysis of covariance (ANCOVA) model with treatment and baseline values included in the model where appropriate. Multiple Imputation (MI) will be used to impute missing data. Details will be provided in the SAP.

11.6.1. Secondary Efficacy Endpoints

The secondary efficacy endpoints are as follows:

- Change from Baseline in percentage of fat in the liver as assessed by MRI-PDFF at Week 12
- Change from Baseline in liver stiffness as assessed by magnetic resonance elastography (MRE) at Week 12
- Change from Baseline of noninvasive liver fibrosis markers (ELF panel) and PRO C3 at Week 12
- Change from Baseline in NFS, APRI, and FIB-4 at Week 12
- Change from Baseline in TG, TC, HDL-C, LDL-C, adiponectin, and ApoA1, B, C3 at Week 12
- Change from Baseline in fasting glucose and insulin, HOMA index (in nondiabetic subjects) and HbA1c in subjects with T2DM at Week 12
- Change from Baseline in fibrinogen, CRP, IL6, IL1 β , TNF- α , TNF- β , alpha2 macroglobulin and haptoglobin levels at Week 12
- Change from Baseline in body weight at Week 12
- Change in waist to hip WTH ratio at Week 12
- Pharmacodynamic parameters of EDP-305: FGF19, C4, and bile acid (BA) at Week 12

Each endpoint will be summarized using an 8-number summary. Subjects in the efficacy population will be included. Comparisons of treatment arms will be performed using an ANCOVA model with treatment and baseline values included in the model where appropriate.

11.7. Safety Endpoints

11.7.1. Adverse Events

The primary safety endpoint of the study is the frequency of AEs, SAEs, and AEs leading to discontinuation through Week 12.

Adverse events will be summarized by the Medical Dictionary for Regulatory Activities (MedDRA) system organ class and preferred term by treatment group. All subjects in the safety analysis set will be included in the summaries. No statistical testing will be performed.

Summaries of AEs will include the following:

- An overall summary of AEs with a line for each of the categories provided below:
- Treatment-emergent AEs
- Treatment-emergent treatment-related AEs
- Treatment-emergent AEs leading to study drug discontinuation
- SAEs
- Treatment-related SAEs
- AEs leading to death

11.7.2. Clinical Laboratory Data

Summaries of clinical laboratory results will be performed using an 8-number summary by visit and treatment. All subjects in the safety population will be included in these summaries.

The number and percentage of subjects with treatment-emergent laboratory abnormalities will be summarized by treatment group. In addition, shift from baseline tables will be generated by visit and treatment group.

11.7.3. Electrocardiogram Data

Electrocardiogram data will be summarized using an 8-number summary by visit and treatment. In addition, the number and percentage of subjects with significant changes in ECG parameters will be summarized by treatment. No statistical testing will be performed.

11.7.4. Vital Signs

Vital signs data will be summarized using an 8-number summary by visit and treatment. In addition, the number and percentage of subjects with significant changes in vital signs will be summarized by treatment. No statistical testing will be performed.

